4.2.3. Choice of Contraception/Barrier Requirements

Nonclinical studies suggest risk for severe manifestations of developmental toxicity at relevant clinical exposures for sasanlimab. There are no nonclinical studies to date with PF-07265028, but because its mechanism of action is to cause immune activation, fetal toxicity cannot be ruled out. Therefore, the use of a highly effective method of contraception is required (see [Appendix 4](#)).

4.2.4. Collection of Retained Research Samples

Retained Research Samples will be collected and stored for further analyses which may, for example, provide greater understanding of the study intervention.

4.3. Justification for Dose

4.3.1. Starting Dose in Monotherapy and Combination

Part 1A: The proposed clinical starting dose for the monotherapy is 25 mg QD based on the totality of toxicity data, pharmacology assessments, and benefit/risk analysis related to PF-07265028.

In the 1-month GLP toxicity study, the HNSTD in cynomolgus monkey is 15 mg/kg, and the one-sixth of the HED is 50 mg QD. No test article-related mortality was observed in mice, and therefore the STD10 (severely toxic dose) is greater than the highest administered dose of 30 mg/kg/day, for which the 1/10th of the HED is 15 mg QD. The key target organ toxicities identified in the 1-month GLP toxicity studies are considered to be monitorable and reversible.

- Nonclinical data supported that the cynomolgus monkey is a pharmacologically relevant species for HPK1 inhibition and may be more relevant to the prediction of the pharmacological effects of PF-07265028 in humans.
- CCI [REDACTED]
- Furthermore, oral administration of PF-07265028 to cynomolgus monkeys was demonstrated to result in both the activation and proliferation of T cell.
- In contrast, in vitro experiments on mouse T cells did not result in enhanced proliferation as was observed on human T cells.

In vitro human cytokine release assays and in vivo cytokine evaluation in the cynomolgus monkey suggest that there is low risk of acute CRS following the administration of PF-07265028.

A starting dose of 25 mg QD was considered to present favorable benefit/risk. The projected $C_{ave,ss}$ or AUC_{ss} in human at 25 mg QD results in 11x and 4x safety margin relative to the $C_{ave,ss}$ or AUC_{ss} at NOAEL in mouse and HNSTD in cynomolgus monkey respectively (Table 6). The respective exposure margins are considered adequate for a starting dose treating participants with advanced cancer.

CCI
[Redacted]

Collectively, the nonclinical data and supportive PK/PD evaluations support the use of 25 mg QD as the starting dose of PF-07265028.

Table 6. Predicted Exposure Margins and Pharmacological Effect for Different Human Starting Dose

Starting Dose (mg QD)	Predicted Exposure Margin				CCI
	Mouse		Monkey		
	$C_{ave,ss}$	$C_{max,ss}$	$C_{ave,ss}$	$C_{max,ss}$	
15	18x	25x	6x	5x	
25	11x	15x	4x	3x	
50	5x	7x	2x	2x	

N=6 mice per group/timepoint (3 male, 3 female); N= 6 monkeys per group (3 male, 3 female)
Mouse and monkey exposure data were from 1-month GLP toxicity study.

Part 1B: Sasanlimab has been shown to be safe and tolerable in humans when administered at 300 mg Q4W. The first dose level for PF-07265028 to be evaluated in Part 1B in combination with sasanlimab 300 mg Q4W SC, will be based on emerging PK/PD and safety data from Part 1A (eg, exposure of PF-07265028, target engagement and/or evidence of biomarker modulation/biologic activity) and will start at a monotherapy dose that is at least one dose level lower than the previously tolerated monotherapy dose (N-1). The initiation of Part 1B at a dose that at least is one dose level lower than tested safe in Part 1A is intended to accelerate evaluation of potentially efficacious combination doses based on predicted minimum biological activity and safety based on predicted potential for overlapping irAE profiles.

4.3.2. Criteria for Dose Escalation

BLRM guided by the EWOC principle will be used in dose escalation. See Section 9.3.1 and Appendix 11 for more details on the model. Using DLT data at all tested dose levels and pre-specified prior distribution of model parameters, posterior probabilities of having a DLT falling into 3 dosing intervals (underdosing, target dosing, overdosing) will be calculated for all dose levels. In general, a dose may only be used for newly enrolled participants if the risk of excessive toxicity (ie, toxicity higher than 0.33 at that dose is less than 25%). The provisional dose levels to be evaluated are listed in Table 7.

Table 7. Provisional Dose Levels for PF-07265028 in Monotherapy Escalation

DL	Dose [mg QD] ^a
DL1 (Starting Dose)	25
DL2	50
DL3 ^b	80
DL4 ^b	125

- The proposed doses may be modified during the study based on the emerging safety and PK data and the dosing frequency may be modified to continuous BID. Intermediate or lower doses may be considered when deemed necessary based on ongoing evaluation of safety and toxicity data. For BID dosing, the total daily dose/ dose increase for the next dose level will be similar (as tablet size allows) regardless of dosing schedule, if it satisfies the EWOC criterion.
- Dose increment from DL2 to DL3 and above may be up to 60% based on BLRM, until MTD/RDE is determined.

Dose escalation will stop when stopping criteria are met (see [Section 9.3.2](#)). In an unlikely situation of observing DLT(s) at the starting dose level, lower dose levels might be considered. The dose level will be recommended by BLRM in such a way that EWOC criteria are fulfilled. The decision of the recommended dose for a new cohort will be jointly made by the investigators and the sponsor. A dose based on a slightly higher EWOC threshold (eg, 30%) or a dose lower than the one recommended by BLRM may be considered if it is deemed safe and appropriate by an overall safety data review.

4.3.3. DLT Definition

A participant is classified as DLT-evaluable if the participant either 1) received at least 75% of the planned doses of the study intervention and have received all scheduled safety assessments during the DLT-observation period (Cycle 1 [28 days]) or 2) have experienced a DLT regardless of the percentage of planned doses received. The percentage of drug received is calculated as the percentage of the actual total amount of drug(s) administered during the DLT-observation period in relation to the planned total amount of drug(s) to be administered for the DLT-observation period. If a participant fails to meet these criteria, the participant is deemed non-evaluable for a DLT, and may be replaced. The sole exception to criterion 1 above is if the participant has missed a minority of safety assessments due to emergency situations (eg, site accessibility issues, inability to go to an external lab, etc). In such cases, the DLRM Committee may judge the participant evaluable, depending on the abundance of the available data.

For the purpose of dose escalation, all treatment-emergent AEs meeting the definition of DLT occurring in the first cycle of treatment (within 28 days of the first dose or until the participant receives the first dose of the second treatment cycle in the event of treatment delays) will be considered DLTs unless they are clearly attributable to underlying disease or intercurrent illness.

Severity of AEs will be graded according to CTCAE version 5.0. For those AEs involving a worsening of a baseline abnormality, a DLT must represent a clinically significant (in the opinion of the Investigator after discussion with the sponsor) shift from baseline.

4.3.3.1. Hematological DLTs

- Grade >3 neutropenia lasting >7 days;
- Febrile neutropenia, defined as an ANC <1000/mm³ with a single temperature of >38.3°C [101°F], or a sustained temperature of ≥38°C [100.4°F] for more than 1 hour.
- Grade >3 neutropenia with infection;
- Grade 3 thrombocytopenia associated with a Grade ≥2 bleeding event; (for bleeding events with no grading available, clinically significant bleeding is defined as requiring hospitalization or urgent medical intervention).
- Grade 3 thrombocytopenia requiring transfusion (Japan only).
- Grade 4 thrombocytopenia;
- Grade 4 anemia (Japan only: Grade 3 anemia requiring transfusion).

4.3.3.2. Non-Hematological DLTs

- Any treatment-emergent Grade >3 non-hematologic toxicity
- Hepatic toxicity events consistent with Hy's Law, ie,
 - >3-fold elevations above the ULN of ALT or AST AND
 - >2 × ULN elevation of serum total bilirubin without alternative explanation (eg, cholestasis or Gilbert's syndrome) AND
 - Absence of initial findings of cholestasis (eg, elevated serum ALP) AND
 - Absence of other reason(s) to explain the combination of increased ALT or ALP and TBili, such as viral hepatitis A, B, or C; preexisting or acute liver disease; or another drug capable of causing the observed injury.
- For participants with Grade 2 hepatic transaminase or alkaline phosphatase levels at baseline as a result of liver metastasis or bone metastasis, a hepatic transaminase or alkaline phosphatase level >10 × ULN.
- Grade 3 fatigue lasting ≥5 days.
- Grade ≥3 nausea/vomiting or diarrhea lasting ≥3 days despite adequate anti-emetic and other supportive care.
- Grade ≥3 CRS of any duration.

- Grade 3 QTcF prolongation:
 - In an asymptomatic participant, the following assessment and confirmation procedure is required: repeat testing, reevaluate by a qualified person, and correct reversible causes (such as electrolyte abnormalities or hypoxia). If, after correction of any reversible causes, the Grade 3 QTcF prolongation persists, then the event should be considered a DLT.
- Any Grade 4 QTcF prolongation.
- Treatment-emergent AEs resulting in failure to deliver 75% of doses of the first cycle doses of PF-07265028 and sasanlimab.
- Grade 5 event unless attributed to a cause clearly not related to study treatment.

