4.3.3.3. Other DLTs

- Clinically important, persistent treatment-emergent toxicities that occur the DLT period (Cycle 1) that are not included in the above criteria may also be considered a DLT following review by the investigators and the sponsor.

The following AEs will not be adjudicated as DLTs:

- Isolated Grade 3 laboratory abnormalities that are not associated with clinical sequelae and are corrected with supplementation/appropriate management within 72 hours of their onset.
- Grade ≥ 2 endocrinopathy controlled by hormonal replacement.
- Grade ≤ 3 injection reaction or allergic reaction is not a DLT (unlikely to be dose-related, but all available information on these events will be collected).
- Grade 3 AE of tumor flare (defined as local pain, irritation or rash localized at sites of known or suspected tumor).

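### As printed, the base non-hematologic DLT line starts above Grade 3, so unlisted Grade 3 events are not automatic DLTs; Grade ≥3 was probably meant, and the exceptions need marking

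*Protocol*

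**What the plan says.** Protocol 4.3.3 makes any treatment-emergent event that meets the definition in Cycle 1 a DLT unless it is clearly due to underlying disease or intercurrent illness. The non-hematologic criteria in 4.3.3.2 are a flat list with no order of precedence:

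- The general line: "Any treatment-emergent Grade >3 non-hematologic toxicity".
- Lines with their own conditions: "Grade 3 fatigue lasting ≥5 days"; "Grade ≥3 nausea/vomiting or diarrhea lasting ≥3 days despite adequate anti-emetic and other supportive care"; Grade 3 QTcF prolongation, which in an asymptomatic participant must persist after reversible causes are corrected; and a threshold above 10 × ULN "For participants with Grade 2 hepatic transaminase or alkaline phosphatase levels at baseline as a result of liver metastasis or bone metastasis".
- A dose-delivery line: "Treatment-emergent AEs resulting in failure to deliver 75% of doses of the first cycle doses of PF-07265028 and sasanlimab".

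Section 4.3.3.3 adds that clinically important, persistent toxicities outside the list "may also be considered a DLT following review by the investigators and the sponsor". It then names events that are not to be DLTs, including "Isolated Grade 3 laboratory abnormalities that are not associated with clinical sequelae" that are corrected within 72 hours, Grade 3 tumor flare, and injection or allergic reactions up to Grade 3.

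SAP 6.1.1 refers back to Protocol 4.3.3 without restating or correcting the line. It leaves the final determination to the investigators and the sponsor at the dose level review meeting.

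**The concern.** The DLT list supplies the data for the Bayesian logistic regression model (BLRM). If the general line starts above Grade 3, a Grade 3 organ toxicity that is not named has no automatic route into the model. Whether it counts depends on when in the cycle it occurs, how long dosing is held, and case-by-case review. With cohorts of about 3 in a first-in-human trial, how one event is classified can decide an escalation step.

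If ≥3 was meant, a smaller drafting problem remains. The word *any* would then take in Grade 3 fatigue of 1 to 4 days, Grade 3 nausea, vomiting or diarrhea of 1 to 2 days, and corrected asymptomatic Grade 3 QTcF prolongation, all of which their own lines leave out. Protocol 2.2.7 names gastrointestinal toxicity among the key expected findings, so this overlap lies where events are plausible.

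**Working it through.** **1. Which sign was intended.** The sign ≥ prints correctly in the fatigue, gastrointestinal and CRS lines of the same list, so the text alone does not show that > is an artefact. The exclusions in 4.3.3.3 point the other way. Removing isolated Grade 3 laboratory changes, Grade 3 tumor flare and Grade ≤3 injection or allergic reactions is natural if Grade 3 events count by default. Under >3, those exclusions would only limit the 75% line and discretionary review. The likelier intention is ≥3.

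**2. What the 75% line catches (once-daily dosing, 28 doses).** The threshold is 0.75 × 28 = 21 doses.

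- By count, restarting at the same dose with no other missed dose: a 7-day hold gives 21/28 = 75.0% (not met); an 8-day hold gives 20/28 = 71.4% (met).
- By amount: 4.3.3 says "The percentage of drug received is calculated as the percentage of the actual total amount of drug(s) administered during the DLT-observation period" against the planned total. An in-cycle dose reduction can then trigger the line after a shorter hold. For 80 mg held 3 days from Day 15 and resumed at 50 mg, (14×80 + 11×50)/(28×80) = 1670/2240 = 74.6% (met).
- If the first missed dose is on Day 22 or later, at least 21 full doses have been given. Delivery is therefore at least 75.0% by count or amount, and the line cannot trigger.

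Example: Grade 3 pneumonitis with the first missed dose on Day 23 has 22/28 = 78.6% delivered. The table in Protocol 10.3.5 requires permanent discontinuation, yet as printed the event is a DLT neither by grade nor by the 75% line.

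**3. Effect on escalation, Part 1A model.** Inputs from Protocol 10.11.1 and 10.11.2: logit π(d) = log α + β log(d/600), log α ~ N(−1.386, SD 2), log β ~ N(0, SD 1), correlation 0. Posteriors are by numerical integration.

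Reproduction of Table 16, prior P(π ≥ 0.33): 25 mg 0.071 to 0.072 depending on the grid (stated 0.071); 125 mg 0.137 (0.135); 500 mg 0.316 (0.317).

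The table below gives the posterior P(π ≥ 0.33) at the next dose, limit 0.25, with assumed cohorts of 3 and no DLT in earlier cohorts.

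| Unlisted Grade 3 events | Next dose | Not counted | Counted | Decision changes? |
|---|---|---|---|---|
| 1 of 3 at 25 mg | 50 mg | 0.019 | 0.329 | Yes |
| 1 of 3 at 50 mg | 80 mg | 0.009 | 0.159 | No |
| 2 of 3 at 50 mg | 80 mg | 0.009 | 0.492 | Yes |
| 1 of 3 at 80 mg | 125 mg | 0.007 | 0.111 | No |
| 2 of 3 at 80 mg | 125 mg | 0.007 | 0.370 | Yes |

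In the first row, the 0.5 weight for equivocal events (10.11.3) gives 0.156, so 50 mg stays open. If the event is counted in full, 25 mg itself remains usable (0.232). One more event-free participant there (1 of 4) brings the value for 50 mg to 0.241, below the limit; 1 of 6 gives 0.133.

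**The case against.** The strongest case against is that no defect is established. The sign may be a reading artefact. If it is not, the list is still coherent: Grade 4 and 5 events count, selected Grade 3 events count under conditions, and the rest go to review. If ≥3 was meant, a reader would let the specific lines govern the general one. There are also several safety nets: the discretionary clause in 4.3.3.3, the final decision at the dose level review meeting (SAP 6.1.1), the 0.5 weighting, and the freedom to choose a dose below the BLRM recommendation (4.3.2).

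Part of this stands. A Grade 3 pneumonitis that ended treatment would reach the review. A specific-over-general reading resolves most of the overlap under ≥3. The pneumonitis example and the model figures also belong to different settings: Protocol 6.5.1 introduces the 10.3.5 guidance for sasanlimab immune-related events, whereas the figures are for Part 1A monotherapy, where Table 8 has Grade 3 toxicity withheld and then resumed. The Part 1B model is in a Technical Supplement that is not part of these documents, so no effect is shown there.

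It does not remove the point. The safety nets are discretionary and do not supply a rule. Because 4.3.3.3 itself signals ≥3, restoring that sign carries out the protocol's own apparent intent and is not merely a reviewer's preference.

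A reader might also infer that in Part 1B the 75% line requires a shortfall in both drugs, and so could never be met once the single Day 1 sasanlimab dose is given. That reading is strained. SAP 6.8.3 computes compliance separately for each drug, which suggests that either shortfall suffices.

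**Conclusion.** The point holds in limited form. As printed, Grade 3 non-hematologic events not named in 4.3.3.2 fall outside the automatic definition, and the 75% line cannot catch one whose first missed dose is on Day 22 or later. The text of 4.3.3.3 indicates that this was not intended. If the source document reads ≥3, only the unmarked exceptions remain.

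The size is modest. With cohorts of 3 and clean earlier cohorts, a single event changes the Part 1A decision only at 25 mg, and one further event-free participant would reopen 50 mg. Later reversals need two such events among three, with the review counting neither. A reader might infer that the protocol excludes Grade 3 organ toxicity from being a DLT, or that escalation would generally proceed in spite of it. The documents support neither: such events may be adjudicated as DLTs, and the model output alone does not set the dose.

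Assumptions: once-daily dosing, no dose missed before the event, cohorts of 3, and the Part 1A prior. The documents give no Grade 3 event rate, so how often this would arise is unknown. It is worth fixing because the repair is simple and bears on safety.

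**What to change.** Check the sign in the source document for this line and for the two neutropenia lines in 4.3.3.1 that also print >3. Consistent with 4.3.3.3, set the general line at Grade ≥3 and end it with an except-as-specified-below clause. List as exceptions:

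- Grade 3 fatigue lasting less than 5 days;
- Grade 3 nausea, vomiting or diarrhea lasting less than 3 days with adequate supportive care;
- asymptomatic Grade 3 QTcF prolongation that does not persist after correction of reversible causes;
- transaminase or alkaline phosphatase up to 10 × ULN in participants with a Grade 2 baseline from liver or bone metastasis;
- the existing 4.3.3.3 exclusions.

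If the source already reads ≥3, only the exception wording is needed. Stating that in Part 1B a shortfall in either drug meets the 75% line is an optional clarification.

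The cost is protocol wording, with no added visits or participants. If the source truly reads >3, the change widens the definition: somewhat more events may count, escalation may be slower, and the assumed DLT rate of 0.2 at 600 mg and the operating-characteristic simulations should be rechecked.

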4.3.3.3. Other DLTs

- Clinically important, persistent treatment-emergent toxicities that occur the DLT period (Cycle 1) that are not included in the above criteria may also be considered a DLT following review by the investigators and the sponsor.

The following AEs will not be adjudicated as DLTs:

- Isolated Grade 3 laboratory abnormalities that are not associated with clinical sequelae and are corrected with supplementation/appropriate management within 72 hours of their onset.
- Grade ≥ 2 endocrinopathy controlled by hormonal replacement.
- Grade ≤ 3 injection reaction or allergic reaction is not a DLT (unlikely to be dose-related, but all available information on these events will be collected).
- Grade 3 AE of tumor flare (defined as local pain, irritation or rash localized at sites of known or suspected tumor).

4.3.4. MTD Definition

The MTD is defined as the highest dose not expected to cause DLT in more than 33% of the treated participants in the first cycle. The target interval for the DLT rate is defined as (0.16, 0.33).

For any given participant that is on-treatment at dose levels that are subsequently considered to be above the MTD, the option to dose reduce will be discussed. If a participant tolerated the above MTD dose level well and is benefiting from therapy, continuation of treatment at the above MTD dose level will require re-consenting.

4.3.5. RP2D Definition

The RP2D is the dose chosen for further investigation based on the Phase 1 study results. The recommended RP2D is based on an integrated assessment of target engagement/attainment, efficacy, safety and pharmacokinetic/ pharmacodynamic (PK/PD) relationship. This integrated approach may result in a RP2D lower than the MTD if supported by the careful consideration of the data generated during dose escalation and demonstrated favorable risk-benefit profile. This may result in a different RP2D dose and schedule being identified for monotherapy and for combination with sasanlimab, as well as for specific tumor indications.

4.4. End of Study Definition

A participant is considered to have completed the study if he/she has completed all periods of the study, including the long-term safety follow-up visits, or death whichever comes first.

The end of the study is defined as the date of the last visit of the last participant in the study or 24 months after the last participant receives their first dose, whichever occurs first. The study may also be terminated at any time at the discretion of the sponsor.

5. STUDY POPULATION

This study can fulfill its objectives only if appropriate participants are enrolled. The following eligibility criteria are designed to select participants for whom participation in the study is considered appropriate. All relevant medical and nonmedical conditions should be taken into consideration when deciding whether a particular participant is suitable for this protocol.

Prospective approval of protocol deviations to recruitment and enrollment criteria, also known as protocol waivers or exemptions, is not permitted.

5.1. Inclusion Criteria

Participants are eligible to be included in the study only if all of the following criteria apply:

Age and Sex:

1. At least 18 years of age (20 years for Japan).
- Refer to [Appendix 4](#) for reproductive criteria for male ([Section 10.4.1](#)) and female ([Section 10.4.2](#)) participants.

Type of Participant and Disease Characteristics:

2. Participants who are willing and able to comply with all scheduled visits, treatment plan, laboratory tests, lifestyle considerations, and other study procedures.

3. **Part 1A Monotherapy:** Histologically or cytologically confirmed advanced or metastatic solid tumors which have progressed following systemic anticancer therapies, or are resistant to standard therapy or for which no standard therapy is available, or for whom standard therapy is not tolerated.
4. **Part 1B Combination Therapy:** Histologically or cytologically confirmed advanced or metastatic solid tumor which have progressed following systemic anticancer therapies, including at least 1 checkpoint inhibitor and displayed primary resistance to checkpoint inhibitors. Primary resistance is defined as having received a checkpoint inhibitor for greater than or equal to 6 weeks with confirmed PD at least 4 weeks after initial PD or SD for less than 6 months. Immunotherapy naïve/secondary PDx-resistant tumors may be considered after discussion with the sponsor.
5. **Part 2 Dose Expansion:** Histologically or cytologically confirmed advanced or metastatic malignancies, including gastric/GEJ cancer, HNSCC, or UC (NSCLC and other solid tumors may be explored based on emergent data from Part 1 and must have histologically or cytologically confirmed advanced or metastatic disease) who have progressed following systemic anticancer therapies, including at least 1 CPI and displayed primary resistance to therapy with checkpoint inhibitors. Primary resistance is defined as having received a checkpoint inhibitor for greater than or equal to 6 weeks with confirmed PD at least 4 weeks after initial PD or SD for less than 6 months. In addition PDx naïve solid tumors may be evaluated based on emergent data from Part 1.
 - Note: The requirement for prior CPI therapy will not be applicable if a cohort of immunotherapy naïve/secondary PDx-resistant tumors warrants further investigation based on Part 1.

Informed Consent:

6. Capable of giving signed informed consent as described in [Appendix 1](#), which includes compliance with the requirements and restrictions listed in the ICD and in this protocol.

Other Inclusion Criteria:

7. ECOG PS \leq 1.
8. Life expectancy \geq 3 months.
9. Adequate hematologic function, including:
 - Absolute neutrophil count \geq 1,500/ μ L;
 - Platelet count $>$ 100,000/ μ L;

- Hemoglobin >9 g/dL.

Note: Transfusions and growth factor support to achieve inclusion are not permitted within 14 days prior to enrollment.

10. Adequate renal function, including:

- Creatinine clearance ≥ 60 mL/min calculated using the Cockcroft-Gault formula.

11. Adequate liver function, including:

- Total bilirubin $\leq 1.5 \times$ ULN unless the participant has documented Gilbert's syndrome;
- AST and ALT $\leq 1.5 \times$ ULN; ($\leq 5.0 \times$ ULN if there are liver metastases);
- Alkaline phosphatase $\leq 2.5 \times$ ULN ($\leq 5 \times$ ULN if there are bone metastases).

12. Have measurable disease per RECIST version 1.1. Lesions previously irradiated are considered measurable if progression has been demonstrated in such lesions.

13. Resolved acute effects of any prior therapy to baseline severity or CTCAE Grade ≤ 1 except for AEs not constituting a safety risk by investigator judgment.

14. Pre-treatment tumor tissue:

- All participants must provide archival FFPE tumor tissue that is of diagnostic quality and representative of their diagnosed malignancy.

- i. **Part 1:** If archival sample is older than 6 months, the participant must consent to undergo a fresh biopsy during the screening period if it can be performed safely. If a new biopsy represents a significant risk in the opinion of the investigator, the participant may be considered for enrollment, after discussion with the sponsor.
 - ii. **Part 2 and mandatory biopsy dose levels of Part 1:** Fresh tumor biopsy during screening is required unless there is archival tissues less than 3 months old and was obtained subsequent to the last systemic anti-cancer therapy and can be performed safely. If a new biopsy represents a significant risk, the participant may be considered for enrollment, after discussion with the sponsor.
15. **On-treatment biopsy:**
 - a. **Part 1:** Starting with DL3 or higher dose, participants may be asked to provide mandatory fresh pre-treatment and on-treatment biopsy. Consent for these procedures will occur during screening.
 - b. **Part 2:** Paired on-treatment biopsies will be mandatory for a subset of participants. Consent for these procedures will occur during screening. On-treatment biopsies are optional and encouraged for all other participants.
16. Participants undergoing biopsies must have at least 1 lesion not identified as a target lesion that can be safely biopsied.
17. Females of childbearing potential must have a negative pregnancy test within 72 hours of first dose of study treatment.

